9.7.1, Visit Windows	New row for study re-entry was added.	
  
 Visit or Procedure	Visit Window and/or Interval	
   
  IP Re-Initiation/ Study Re-Entry (When a subject has previously discontinued treatment/ withdrawn consent and has chosen to return to study participation) 	 Day 0 procedures should be conducted and the visit window will be relative to Day 0 from the original study entry. 	
  
	Visit or Procedure	Visit Window and/or Interval	IP Re-Initiation/ Study Re-Entry (When a subject has previously discontinued treatment/ withdrawn consent and has chosen to return to study participation)	Day 0 procedures should be conducted and the visit window will be relative to Day 0 from the original study entry.	Clarification of study procedures for subjects who re-enter the study.															
Visit or Procedure	Visit Window and/or Interval																					
IP Re-Initiation/ Study Re-Entry (When a subject has previously discontinued treatment/ withdrawn consent and has chosen to return to study participation)	Day 0 procedures should be conducted and the visit window will be relative to Day 0 from the original study entry.																					
9.7.15. Early Discontinuation and/or Early Termination Procedures for Subjects that Withdraw from Investigational Product or Withdraw Consent	Subjects that discontinue investigational product are expected to continue in the study until the end of the study, and the study will only terminate at the time when the needed number of adjudicated events has accrued or at the discretion of the Sponsor.	Subjects who discontinue investigational product are expected to continue in the study until the end of the study, and the study will only terminate at the time when the needed number of adjudicated events has accrued or at the discretion of the Sponsor. In general, subjects should be strongly encouraged to both stay on investigational product and remain in the study until study termination. Even if a subject is no longer receiving investigational product, if the subject is attending study visits or participating in study follow-up (through telephone visits or electronic medical record review), their information will contribute to the study primary endpoint and the evaluation of clinical benefit of OCA. All information collected in the study during regular study visits and through subjects participating in follow-up will contribute to the evaluation of safety of OCA and the scientific and medical understanding of PBC.		Please refer to earlier justification for this change.																		
	A new footnote (footnote b) was to Table 8.	
  
 Table 8: Early Discontinuation Scenarios	
 
 	Investigational Product	Consent	Study Visit Status	EOT Visit^a	EOS Visit^a	
   
 Early Termination^b	Discontinued	Withdrawn	No additional visits except EOT/EOS	Combined Visit, Completed as close as possible to last dose IP	
  
		Table 8: Early Discontinuation Scenarios							Investigational Product	Consent	Study Visit Status	EOT Visit ^a	EOS Visit ^a	Early Termination ^b	Discontinued	Withdrawn	No additional visits except EOT/EOS	Combined Visit, Completed as close as possible to last dose IP		Please refer to earlier justification for this change.
Table 8: Early Discontinuation Scenarios																						
	Investigational Product	Consent	Study Visit Status	EOT Visit ^a	EOS Visit ^a																	
Early Termination ^b	Discontinued	Withdrawn	No additional visits except EOT/EOS	Combined Visit, Completed as close as possible to last dose IP																		

Section	Original Text (Amendment 5, 04 Jan 2018)	Revised Text (Version 6, 05 Nov 2019)					Justification for Change	
		Treatment Discontinuation ^{b,c}	Discontinued	Active	Regular Visit Schedule	Complete as close as possible to last dose IP	Complete at Final study visit	
	Discontinued	Semiannual contact ^d	Telephone contact every 6 months (± 2 weeks)	Combined Visit, Completed as close as possible to last dose IP				
	Discontinued	Record review only ^d	Record review only	Combined visit Completed as close as possible to last dose IP				
Sponsor Termination	Discontinued	N/A	No additional visits except EOT/EOS	Combined visit Completed as close as possible to last dose IP				
Pregnancy	Interrupted	Retained	Regular Visit Schedule	Complete as close as possible to last dose IP	Complete at Final study visit			
	Discontinued	Complete per the above scenarios - Early Termination or Treatment Discontinuation						
Lost to Follow-up	Discontinued	LTF	None	Unable to complete due to LTF status				

EOS = end of study; EOT = end of treatment; IP = investigational product
 
^a Refer to Section 7.1.1 Schedule of Study Procedures, Table 2 for all procedures and evaluations required at the End of Treatment and End of Study Visits.
 
^b Subjects may choose to re-consent, re-enter the study, and re-initiate IP at a later date. Day 0 procedures will be repeated and the subject will resume in the visit window relative to the original Day 0.
 
^c Includes initiation of commercially available OCA.
 
^d Outcomes data to be discussed or collected include data related to adjudicated hepatic and cardiovascular event-related data. Additional data such as information on concurrent medical conditions, co-morbidities, relevant adverse events, and concomitant medications may be collected to help facilitate adjudication of these post-study events.
								

Section	Original Text (Amendment 5, 04 Jan 2018)	Revised Text (Version 6, 05 Nov 2019)	Justification for Change
9.7.15, Early Discontinuation and/or Early Termination Procedures for Subjects that Withdraw from Investigational Product or Withdraw Consent	New language added.	
During the EOT/EOS Visit:
 
For subjects who prematurely terminate investigational product and/or the study, procedures outlined in Section 8.4.1 should be followed.
 
Subjects who wish to re-initiate investigational product while participating in study follow-up or re-enter the study after having withdrawn consent or having discontinued treatment more than 3 months since the last visit must confirm that they have not received any investigational product being evaluated for the treatment of PBC within 30 days or commercial OCALIVA for three months before restarting investigational product or within 5 half-lives of the compound (whichever was longer). Subjects are to be re-consented and new Day 0 visit procedures must be performed. The subject will resume the study in the visit window relative to their original Day 0 visit.
	Please refer to earlier justification for this change.
12.1.1.5, Suspected Unexpected Serious Adverse Reactions	New section was added.	
A suspected unexpected serious adverse reaction (SUSAR) is defined as a suspected adverse reaction which is assessed as serious, causally related to the investigational product, and unexpected per the reference safety information (RSI) in the Investigator’s Brochure.
 
SUSARs are subject to expedited reporting. The Sponsor shall ensure that all relevant information about SUSARs that are fatal or life-threatening are recorded and reported as soon as possible to the relevant competent authorities (either directly or through the Eudravigilance Clinical Trials Module, as applicable), and to the Ethics Committees, no later than 7 days after knowledge by the Sponsor of such a case. Relevant follow-up information is subsequently communicated within an additional 8 days. All other SUSARs shall be reported to the competent authorities concerned (either directly or through the Eudravigilance Clinical Trials Module) and to the Ethics Committees concerned, within a maximum of 15 days of first knowledge by the Sponsor. Each competent authority shall ensure that all SUSARs to an investigational product which are brought to its attention are recorded. The Sponsor shall also inform all participating Investigators, as applicable to the local regulations.
	Updated AE reporting requirements for SUSARs

Section	Original Text (Amendment 5, 04 Jan 2018)	Revised Text (Version 6, 05 Nov 2019)	Justification for Change
14.1, Study Monitoring	The Investigator may exercise judgment in allowing the CRA access to particular sections of the subject's medical records if these are deemed irrelevant to the performance, observations or conduct of this study.	The Investigator may exercise judgment in allowing the CRA access to particular sections of the subject's medical records if these are deemed relevant to the performance, observations or conduct of this study.	Revision was made to correct a typographical error
17.3, Regulatory Documentation	
 • Form FDA 1572 	
 • Form FDA 1572 or equivalent form for the Investigator's region 	Revision was made for clarification purposes.

ADDENDUM 1 TO PROTOCOL 747-302

Netherlands-specific monitoring of subjects receiving CYP2D6 substrates with a narrow therapeutic index

PURPOSE

To implement additional monitoring by investigators for subjects in the Netherlands receiving CYP2D6 substrates with a narrow therapeutic index, such as tricyclic antidepressants (TCAs), concomitantly with investigational product (obeticholic acid; OCA).

OVERVIEW AND RATIONALE

The following guidance is being provided based on feedback from the Medical Ethics Review Committee overseeing the 747-302 study in the Netherlands. The Committee noted that specific data on drug interactions in subjects receiving CYP2D6 substrates with a narrow therapeutic index, such as TCAs, concomitantly with investigational product (OCA) are limited and recommended the implementation of additional monitoring in subjects who fall into this category.

Currently there is no evidence of clinically meaningful interactions between OCA and CYP2D6 substrates. The current United States Package Insert and European Union Summary of Product Characteristics for Ocaliva[®], in Section 7 and Section 4.5, respectively, include potential interactions with warfarin, CYP1A2 substrates with a narrow therapeutic index, and bile acid binding resins but do not include specific mention of a potential interaction with CYP2D6 substrates with a narrow therapeutic index, consistent with the lack of evidence, at present, of clinically meaningful interactions between OCA and CYP2D6 substrates. However, as data are limited, the Sponsor has agreed to incorporate the requested additional monitoring for subjects in the Netherlands concomitantly receiving TCAs.

All information including, but not limited to, inclusion/exclusion criteria and study procedures provided in the current approved version of the study protocol should continue to be followed, in addition to the guidance provided below as a supplement to protocol Section 9.2 Concomitant Medications.

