
Synopsis, Statistical Methods, Sample Size Justification
 
Section 13.1.2, Determination of Sample Size
	
The following assumptions were used in sample size calculations:
 
 Exponential survival curves, placebo survival estimate of 0.5 at 8 years with a hazard ratio of 0.60, and total study duration of 8 years, allowing for 2 years accrual and 6 years of follow up 
Insertion
 
Based on the randomization ratio, significance level, and assumed hazard ratio, a total of 121 events (both groups combined) will provide 80% power to demonstrate a statistically significant difference between OCA and placebo on time to clinical outcomes.
 
In addition, based on the remaining assumptions stated above, it is estimated that approximately 350 subjects will be enrolled to attain 121 events.
	
The target population is subjects who are at higher risk of liver-related clinical complications. Eligible subjects will have a diagnosis of PBC with bilirubin levels >ULN and ≤5x ULN and/or ALP >3x ULN.
 
The following assumptions were used in sample size calculations:
 
 Exponential survival curves, placebo survival estimate of 0.6 at 8 years with a hazard ratio of 0.60, and total study duration of 10 years (from first subject enrolled), allowing for 4 years of subject accrual and 6 years of follow up. Two interim analyses and one final analysis are planned. The first interim analysis will be performed when 50% of the target events are accrued and the second interim will be performed when 75% of the target events are accrued. A dropout rate of 10% is assumed 
Based on the randomization ratio, significance level, and assumed hazard ratio, a total of 127 events (both groups combined) will provide 80% power to demonstrate a statistically significant difference between OCA and placebo on time to liver-related outcomes, including all-cause mortality.
 
In addition, based on the remaining assumptions stated above, it is estimated that approximately 428 subjects will be enrolled to attain 127 events.
	
Rationale 8
 
Rationale 4
 
Rationale 3

Section	Original Text (Amendment 3, 07 September 2016)	Revised Text (Version 4, 10 May 2017)	Justification for Change

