
Section	Original Text (Amendment 5, 04 Jan 2018)	Revised Text (Version 6, 05 Nov 2019)	Justification for Change
	
adjudicated events has accrued. If a subject reaches an outcome event, he or she should continue the regular visit schedule and continue taking investigational product as long as the subject has not met any of the criteria for mandatory interruption of investigational product outlined in Table 7, and the Investigator assesses it as safe. In general, subjects should be strongly encouraged to both stay on investigational product and remain in the study until study termination
		

7.9, Subject Retention
	
A new section was created.
	
The primary objectives for the end of study analysis are to evaluate the effects of OCA compared with placebo on all-cause mortality and liver-related clinical outcomes. The overall study duration is event driven and will be determined by the time required to observe the prespecified adjudicated events for the clinical outcomes’ composite endpoint (Section 7.1). Therefore, it is critical that subjects continue to participate for the duration of the study to enable assessment of clinical outcomes and confirmation of the clinical benefit of OCA in PBC.
 
Subjects may discontinue investigational product during the study; however, these subjects are expected to continue in the study until study termination and every effort will be made by the investigator to discuss subjects’ continuation in the study. Even if a subject is no longer receiving investigational product, if the subject is attending study visits or participating in study follow-up, their information will contribute to the study primary endpoint and the evaluation of clinical benefit of OCA. All information collected in the study during regular study visits and through subjects participating in follow-up will contribute to the evaluation of safety of OCA and the scientific and medical understanding PBC.
 
Investigators should emphasize to subjects the importance of their continuation in the study even after withdrawal of investigational product and discuss with subjects the various options for continued participation in the study:
 
 • Continuing to attend regularly scheduled visits, or 	
A new section was created to provide guidance on the importance of retaining subjects in the study.

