
Section	Original Text (Amendment 5, 04 Jan 2018)	Revised Text (Version 6, 05 Nov 2019)	Justification for Change
	
– Early termination procedures should be conducted if the subject withdraws consent (See Section 9.7.15).
 
The Investigator is encouraged to contact the Sponsor prior to discontinuing a subject from treatment. The Investigator must notify the Sponsor study monitor by telephone or email as soon as possible if any subject prematurely withdraws from the study.
	
 – Consent may be modified to discontinue study visits, but allow semi-annual telephone contact of subject, subject’s primary care physician, or personal contacts who can provide information on behalf of the subject by the investigator – Consent may be modified to discontinue study visits or semi-annual telephone contact, but may allow for continued access to medical records to assess for suspected major adverse cardiovascular events (MACE), liver-related clinical outcomes, and new interventions and medications for treatment of PBC. – Other subject follow-up options to collect study outcomes should be pursued according to local laws and regulations. If one of these alternate methods to collect study outcomes is acceptable to the subject, then the subject will be deemed not to have withdrawn consent for follow-up. 
Early termination procedures should be conducted if the subject withdraws consent (see Section 9.7.15).
 
The Investigator is encouraged to contact the Sponsor prior to discontinuing a subject from treatment. The Investigator must notify the Sponsor study monitor by telephone or email as soon as possible if any subject prematurely withdraws from the study.
	

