8.4.3, Lost to Follow Up	If a subject fails to return to the clinic for a study visit, and the Investigator ceases to have contact with the subject, he or she will be withdrawn from the study. A reasonable effort must be made to contact the subject and determine the reason(s) why a subject fails to return for a study visit or is lost to follow-up. This information and date of contact must be recorded in the appropriate CRF.	If a subject fails to return to the clinic for a study visit, and the Investigator ceases to have contact with the subject, he or she will be withdrawn from the study. Diligent efforts to determine the reason(s) why a subject failed to return for a study visit or is lost to follow-up must be made. If the subject has provided consent, the subject's primary care physician or personal contacts who can provide information on behalf of the subject by the investigator, must be contacted if the subject consistently fails to return for study visits. This information and date of contact must be recorded in the appropriate CRF.	Revisions were made to provide options for follow up of subjects who discontinue.

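### Section 8.4.3 withdraws a subject once contact ceases and requires no check of death or transplant up to study end, which risks informative censoring of unknown size

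*Protocol*

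**What the plan says.** All Version 6 text below comes from the revised-text column of Appendix K.

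- **Section 8.4.3 (Lost to Follow Up):** a subject fails to return "and the Investigator ceases to have contact with the subject, he or she will be withdrawn from the study". It continues: "Diligent efforts to determine the reason(s) why a subject failed to return for a study visit or is lost to follow-up must be made". Where the subject has consented, the primary care physician or personal contacts "must be contacted if the subject consistently fails to return for study visits", and the information goes into the CRF. Section 8.4.4 repeats the duty to find out why the subject did not return.
- **Section 9.7.15, Table 8:** the lost-to-follow-up row gives study visit status as none, and for the end-of-treatment and end-of-study visits "Unable to complete due to LTF status". The rows for semiannual contact and for record review each name a route that continues.
- **Section 7.9 (Subject Retention):** "it is critical that subjects continue to participate for the duration of the study to enable assessment of clinical outcomes". Subjects who stop product are expected to stay until study termination by visits, telephone or records access. Personal and physician contacts who can report clinical status are requested.
- **Section 8.4.1:** other ways of collecting outcomes should be pursued as local law allows. On agreement to further follow-up it adds: "If one of these alternate methods to collect study outcomes is acceptable to the subject, then the subject will be deemed not to have withdrawn".
- **Section 13.1.2 (Version 4, Appendix I):** "A dropout rate of 10% is assumed", with 127 events from about 428 subjects.

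**The concern.** A subject who asks to stop visits can be followed by telephone or records to the end of the trial. A subject who simply goes silent, without withdrawing consent, is withdrawn. The second subject may have gone silent because of deterioration. All-cause death counts in the primary outcome (Sections 7.9 and 13.1.2), and Section 12.1.6 lists transplant among the clinical outcome events that feed it. Both can be learned from a physician, a relative or a record without the subject.

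If follow-up stops at loss of contact and risk rises afterwards, censoring is related to outcome. If such loss also differs between arms, the hazard ratio is biased, and a larger sample does not repair that. The SAP can choose how to censor, but it cannot analyse events that sites were never told to look for.

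**Working it through.** **1. What each rule requires after contact ceases**

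| Provision | Requires | Does not require |
|---|---|---|
| 8.4.3, 8.4.4 | Efforts to learn the reason; consented physician or personal contact after repeated missed visits | Vital or transplant status; repeat checks; ascertainment to study end |
| Table 8, lost row | Nothing further | Telephone, contact or record route |
| 7.9, 8.4.1 | Telephone, contacts or records, for subjects who agree | Any stated application to a lost subject who agreed earlier |

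A death that occurs after the tracing contact has no required route into the data.

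**2. The plan's own figures**

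Inputs (Section 13.1.2): exponential survival, placebo event-free 0.6 at 8 years, HR 0.60, 4 years' accrual plus 6 years' follow-up, 10% dropout, 80% power. Allocation is 1:1 (Section 7.1). Looks are at 64 and 96 events (Section 13.1.12). Two-sided alpha of 0.05 is my assumption.

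- Fixed-design events (Schoenfeld): 4(1.960 + 0.842)²/(ln 0.60)² = 120.3, so 121.
- With Lan-DeMets O'Brien-Fleming looks (simulated bounds 2.95, 2.35, 2.01), power at 127 events is 0.81, or 0.80 on the Freedman scale.
- Hazards: placebo −ln(0.6)/8 = 0.0639 per year; OCA 0.60 × 0.0639 = 0.0383.
- Event probability with uniform accrual: p = 1 − [exp(−6λ) − exp(−10λ)]/(4λ), giving 0.398 and 0.263, mean 0.331.
- N = 127/0.331 = 384, and 384/0.9 = 427, against the stated 428.

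The figures reproduce.

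**3. Effect on event numbers**

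Worst case for counting, with all lost subjects contributing nothing:

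- 10% lost: 428 × 0.10 = 42.8 subjects; 42.8 × 0.331 = 14.2 events unseen; 428 × 0.9 × 0.331 = 127.4 remain.
- 20% lost: 85.6 subjects; 28.3 events unseen; 113.3 remain. Power is about 0.78 (Schoenfeld, no interims) if the timeline is held fixed.

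At the assumed 10% the planned 127 events are still reached.

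**4. Effect on the hazard ratio (illustration)**

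Simulation of 1,000 trials with the inputs above. A fraction of each arm is lost at a random time, and the hazard after loss is unchanged or tripled. The Cox HR with complete follow-up is compared with the HR when subjects are censored at loss.

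| Lost, placebo / OCA | Hazard after loss | Result |
|---|---|---|
| 10% / 10% | unchanged | about 6 events hidden |
| 10% / 10% | tripled | about 15 events hidden |
| 5% / 15% | tripled | HR 0.648 complete, 0.599 observed (shift 0.049) |
| 15% / 5% | tripled | HR 0.559 complete, 0.595 observed (shift 0.036) |

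The bias can go either way. The tripled hazard and the 5%/15% split are assumptions with no source in the protocol, and the protocol does not say how much of the 10% dropout is loss to follow-up. The rows show what such losses would do; they do not bound the effect.

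**The case against.** A reader might infer that lost subjects get no further follow-up and that their deaths and transplants can never enter the primary endpoint. The documents do not support this. Section 8.4.3 makes tracing mandatory and, with consent, requires contact with third parties. The justification given for the change is "Revisions were made to provide options for follow up of subjects who discontinue". Section 7.9 gathers those contacts because they can report clinical status. Section 12.1.9 (Version 4) requires reporting of serious events within 30 days of leaving the study. Section 13.4 (Version 5) sends all deaths and suspected liver outcomes after first dose to adjudication, with no exception for lost subjects. A death learned in this way would count.

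A reader might also infer that Sections 7.9 and 8.4.3 contradict each other. They do not, literally: the options in 7.9 and 8.4.1 depend on the subject's agreement, and someone who cannot be reached cannot newly agree.

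Three further points stand. Stopping product for pruritus or moving to commercial OCA is treatment discontinuation with continued follow-up, so neither is an example of loss of contact. Operational detail is assigned to a Subject Retention Plan that is not shown, and the censoring rule may properly sit in the SAP. Opt-out record review would also clash with Section 9.7.2 (as revised by Amendment 1), which requires changes in consent status, including record review, to be documented in a signed form.

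What the objection leaves untouched is that the mandated contact is tied to the reason for non-return, and that nothing extends ascertainment to study end.

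**Conclusion.** The point holds in a limited form. Section 8.4.3 and the Table 8 row let outcome ascertainment stop when contact is lost, although consented routes to death and transplant information may still be open. This is a gap against the trial's own retention aim, not a contradiction, and it does not show that events are excluded.

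Planned power is unaffected at the assumed 10% dropout. What remains is possible informative censoring. Its size is unknown: the HR shifts of about 0.05 and 0.04 rest on assumed unequal loss and a tripled hazard after loss. Because the remedy is cheap, the change should be made. Only the last part of the protocol was available, so the judgement rests on the Version 6 text as reproduced in Appendix K.

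**What to change.** In Section 8.4.3 and the lost-to-follow-up row of Table 8:

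- State that loss of contact alone does not end outcome ascertainment.
- For subjects who have not withdrawn consent, use the physician, personal-contact or record routes to which they have already consented, and other sources that local law permits, to check vital and transplant status before each interim analysis and the final data cut.
- Date any event found to its occurrence and send it to adjudication.
- Do not impose record review on subjects who never consented to it.

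Cost: amendment wording, possibly consent-form wording and ethics review for future consents, and a small amount of site work. At the assumed 10% dropout this concerns at most about 43 subjects per check (0.10 × 428 = 42.8).
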